8.2.4. Visit 4 (Week 4/Day 29)

This visit must occur 4 weeks/28 days (± 4 days) after Visit 2.

At this visit, the investigator or designee will perform the following procedures:

1. Query the subject/caregiver in a non-directive manner about any changes in the subject's health since the previous visit and report all AEs on the appropriate form
2. Query the subject/caregiver about any changes in the subject's concomitant therapies since the previous visit and report changes on the appropriate form

3. Confirm the subject continues to comply with all study restrictions, is eligible to continue in the study and has followed all study instructions
4. Measure vital signs
5. Perform a urine pregnancy test for WOCBP
6. Identify any new lesions that require treatment (Treatment Area)
7. Determine BSA of EBS lesions in the Assessment Area and in the Treatment Area (if new lesions exist) using the palmar method; Note: the area being treated may not exceed 30% BSA
8. Perform the IGA evaluation on the Assessment Area
9. Collect blood & urine samples for clinical laboratory tests
10. Dispense, collect and weigh study medication as appropriate
11. Dispense a blister lancing kit and instructions to the subject/caregiver if needed
12. Review the study instructions, including eDiary, use of body charts and approved bland, non-medicated, emollient/ moisturizer use, with the subject/caregiver
13. Schedule Visit 5 for Week 6/Day 43.

The investigator will mark the general location of all the EBS lesions on the appropriate body chart(s) at each study visit.

8.2.5. Visit 5 (Week 6/Days 43)

This visit must occur 6 weeks/42 days (± 4 days) after Visit 2.

At this visit, the investigator or designee will perform the following procedures:

1. Query the subject/caregiver in a non-directive manner about any changes in the subject's health since the previous visit and report all AEs on the appropriate form
2. Query the subject/caregiver about any changes in the subject's concomitant therapies since the previous visit and report changes on the appropriate form
3. Confirm the subject continues to comply with all study restrictions, is eligible to continue in the study and has followed all study instructions
4. Measure vital signs
5. Identify any new lesions that require treatment (Treatment Area)
6. Determine BSA of EBS lesions in the Assessment Area and in the Treatment Area (if new lesions exist) using the palmar method; Note: the area being treated may not exceed 30% BSA
7. Perform the IGA evaluation on the Assessment Area
8. Dispense, collect and weigh study medication as appropriate
9. Dispense a blister lancing kit and instructions to the subject/caregiver if needed
10. Review the study instructions, including eDiary, use of body charts and approved bland, non-medicated, emollient/ moisturizer use, with the subject/caregiver
11. Schedule Visit 6 for Week 8/Day 57.

The investigator will mark the general location of all the EBS lesions on the appropriate body chart(s) at each study visit.

8.2.6. Visit 6 (Week 8/Day 57); end of the treatment period

This visit must occur 8 weeks/56 days (± 4 days) after Visit 2.

At this visit, the investigator or designee will perform the following procedures:

1. Query the subject/caregiver in a non-directive manner about any changes in the subject's health since the previous visit and report all AEs on the appropriate form
2. Query the subject/caregiver about any changes in the subject's concomitant therapies since the previous visit and report changes on the appropriate form
3. Confirm the subject continues to comply with all study restrictions, is eligible to continue in the study and has followed all study instructions
4. Conduct a physical examination
5. Measure vital signs
6. Perform a urine pregnancy test for WOCBP
7. Identify any new lesions that appeared since the last visit
8. Determine BSA of EBS lesions in the Assessment Area and new lesions (if new lesions exist), as well as EBS lesions that are not being treated (e.g. $>30\%$ BSA or lesions that are occluded) using the palmar method
9. Measure the LSA of the Reference Lesion
10. Perform the IGA evaluation on the Assessment Area
11. Collect blood & urine samples for clinical laboratory tests
12. Take standardized color photographs
13. Collect and weigh all study medication as appropriate
14. Dispense a blister lancing kit and instructions to the subject/caregiver if needed
15. Review the study instructions, including eDiary, use of body charts and approved bland, non-medicated, emollient/moisturizer use, with the subject/caregiver
16. Perform ECG
17. Schedule Visit 7 for Week 12/Day 84.

The investigator will mark the general location of all the EBS lesions on the appropriate body chart(s) at each study visit.

8.2.7. Visit 7 (Week 12/Day 85)

This visit must occur 12 weeks/84 days (± 4 days) after Visit 2.

At this visit, the investigator or designee will perform the following procedures:

1. Query the subject/caregiver in a non-directive manner about any changes in the subject's health since the previous visit and report all AEs on the appropriate form
2. Query the subject/caregiver about any changes in the subject's concomitant therapies since the previous visit and report changes on the appropriate form

3. Confirm the subject continues to comply with all study restrictions, is eligible to continue in the study and has followed all study instructions
4. Measure vital signs
5. Perform a urine pregnancy test for WOCBP
6. Identify any new lesions that appeared since last visit
7. Determine BSA of EBS lesions in the Assessment Area and new lesions (if new lesions exist) using the palmar method
8. Calculate the total BSA of all EBS lesions
9. Perform the IGA evaluation on the Assessment Area
10. Dispense a blister lancing kit and instructions to the subject/caregiver if needed
11. Review the study instructions, including eDiary, use of body charts and approved bland, non-medicated, emollient/moisturizer use, with the subject/caregiver
12. Schedule Visit 8 for Week 16/Day 113.

The investigator will mark the general location of all the EBS lesions on the appropriate body chart(s) at each study visit.

8.2.8. Visit 8 (Week 16/Day 113); end of the study

This visit must occur 16 weeks/112 days (± 4 days) after Visit 2.

At this visit, the investigator or designee will perform the following procedures:

1. Query the subject/caregiver in a non-directive manner about any changes in the subject's health since the previous visit and report all AEs on the appropriate form
2. Query the subject/caregiver about any changes in the subject's concomitant therapies since the previous visit and report changes on the appropriate form
3. Confirm the subject continues to comply with all study restrictions, is eligible to continue in the study and has followed all study instructions
4. Measure vital signs
5. Identify any new lesions that appeared since last visit
6. Determine BSA of EBS lesions in the Assessment Area new lesions (if new lesions exist) using the palmar method
7. Calculate the total BSA of all EBS lesions
8. Measure the LSA of the Reference Lesion
9. Perform the IGA evaluation on the Assessment Area
10. Collect blood & urine samples for clinical laboratory tests
11. Perform a urine pregnancy test for WOCBP
12. Take standardized color photographs
13. Perform ECG
14. Discharge the subject from the study.

The investigator will mark the general location of all the EBS lesions on the appropriate body chart(s) at each study visit.

8.3. EBS Lesion Identification

For this study, an EBS lesion is defined as a blister (*i.e.*, a fluid filled thin-walled structure), or the crust and/or erosion arising from a previous blister, and the immediately surrounding intense erythema. At Visit 1 (Week -6), for each subject the investigator will determine if the subject has EBS lesions that fulfill the inclusion criteria.

The EBS lesions must be on one or both of the following body areas:

- Localized involvement:
 - plantar or palmar areas only
 - plantar areas where >25% of the area has hyperkeratosis that has been present for greater than 12 weeks are excluded.
- Generalized involvement:
 - Arms from the shoulder to the tips of the fingers
 - Legs from the hip to the tips of the toes
 - Front and back of the torso, including the neck from the mandibular line in the front and the hairline in the back, to the beltline

The Assessment Area of EBS lesions to be treated must be $\geq 2\%$ and $\leq 30\%$ BSA at Visit 1 (Week -6) for the subject to be enrolled and at Visit 2 (Week 0) for the subject to be eligible for randomization. The area being treated must not exceed 30% BSA at any time.

Between Visit 1 (Week -6) and Visit 2 (Week 0) the status of EBS lesions may change, therefore, at Visit 2 (Week 0), the investigator will evaluate each subject to determine which of the following categories describe the subject's EBS lesions identified at Visit 1 (Week -6):

1. The V1 Assessment Area lesions do not meet the protocol requirements for the subject to be eligible for randomization, and the subject does not have EBS lesions that meet the requirements
2. The V1 Assessment Area lesions meet the protocol requirements for the subject to be eligible for randomization
3. The V1 Assessment Area lesions do not meet the protocol requirements for the subject to be eligible for randomization, but the subject has additional/other EBS lesions that meet the requirements. The Assessment Area is re-defined.

At Visit 2 (Week 0), the investigator will discharge subjects from the study who are in category 1.

At Visit 2 (Week 0), for subjects who are in category 2 or 3 the investigator will follow the procedures below to identify EBS lesions to be treated.

The investigator will mark the general location of all the EBS lesions on the appropriate body chart(s) at each study visit.

8.3.1. Occluded Lesions

The scalp, groin and areas where, in the investigator's opinion, the study medication might become occluded are excluded from treatment with study medication.

8.4. Subject Instructions

An investigational center staff member will dispense the following items to each subject/caregiver to help with compliance to the study requirements as needed at a specified visit schedules

- Subject Instruction Sheet, and blister lancing instructions
- eDiary instructions and body charts.

Updated information and instruction for subjects will be provided as necessary.

Throughout the study, the subjects should:

- Continue their routine cleansing regimen; however, products that, might affect the signs or symptoms of EBS being evaluated (*e.g.*, medicated cleansers, MediHoney, Silvadine cream 1%, CBD oil, etc.) are prohibited. The investigator should consult with the Medical Monitor for discussion on any moisturizers or therapies in question that are not directly specified in the protocol.
 - Subjects with evening bathing habits (*e.g.* pediatric patients), should bathe prior to study medication application and modify evening habits such that sufficient time is left to allow for at least 1 hour before dressing the lesions (if applicable), wearing clothing or retiring to bed to allow for absorption of medication. Loose fitting garments (*e.g.* robes) that do not rub against the treated areas are acceptable within the hour.
- Continue their routine cosmetics and skin care products
- Avoid exposing the treated EBS lesions to excessive natural or artificial ultraviolet radiation (*e.g.*, sunlight, tanning beds) and use sunscreen on the lesions, if excessive exposure cannot be avoided
- Apply study medications to lesions identified by the Investigator that require treatment as described in section 7.5.4:
 - If the lesion is identified as part of the Assessment area, apply study medication to the lesions daily, in the evening, **regardless of lesion resolution**
 - If the lesion is NEW (appears after Visit 2), apply study medication to the lesion **until lesion resolution**
 - Make note using subject body charts any NEW lesions requiring treatment that appear in between study visits (not to exceed 30% BSA)

- Not wear tight clothing or retire to bed for at least 1 hour post application to allow for absorption of medication.
- Use only a bland, non-medicated emollient/moisturizer or routine cleansing products (e.g. Emu oil, Aquaphor, bleach baths, topical antiseptics) to treat EBS lesions as described in sections 7.5.3 & 7.5.4
- For at least 6 hours after a study medication application, DO NOT:
 - Wash/submerge the treated EBS lesions
 - Apply any topical products to the treated EBS lesions
 - Participate in any activity that might result in profuse perspiration (e.g., vigorous exercise, saunas, steam rooms, etc.).
- Follow the instructions for blister lancing management and care
- Bring the subject instruction sheet and all study medication tubes with them to each visit.

On study visit days, the subjects should:

- Wear appropriate clothing to ease the photography procedures
- Starting with Visit 3 (Week 1), not apply the study medication or any topical products to the treated EBS lesions within 6 hours prior to a study visit.

8.5. EBS Lesion Care

8.5.1. Blister lancing kit

At Visits 1-7, an investigational center staff member will dispense a blister lancing kit(s) and instructions to every subject/caregiver as appropriate. The subject will be instructed to lance all EBS lesions, including study medication treated lesions and those not treated with study medication (e.g., lesions on the face), within 24 hours of appearance.

Blister lancing kits and written instructions for use of the kits will be provided to each investigational center prior to the initiation of subject enrollment.

8.5.2. Bandaging/Dressing Use

The following section applies to all EBS lesions. Bandaging may be a part of a subject's routine lesion care. Because EB skin may be more fragile in the heat and humidity and due to the fact that there is considerable variation in how and when lesions are dressed and the types of dressings used, subjects should generally be discouraged from bandaging their lesions during their participation in the study. However, bandaging is not prohibited provided the subject maintains their current bandaging routine and remains consistent throughout their participation in the study. Subjects should indicate their bandaging routine which will be recorded in the eCRF as follows:

- 1) The subject never bandages their EBS lesions
- 2) The subject occasionally bandages their EBS lesions when:
 - a. The lesion requires protection from further trauma or contact and friction from clothes.
 - b. The lesion is draining or bleeding.
 - c. The lesion is painful, and a dressing may improve comfort.
- 3) The subjects always bandages their EBS lesions

Note: All bandaging is prohibited for the first hour after study medication application

In general, the types of dressings to be used for the study should be minimally absorptive, non-adhesive (to the skin), not-intended to treat the wounds (i.e. antimicrobial, honey, keratin, collagen and/or impregnated dressings) and used in a manner that, based on the subject's experience, do not promote new lesion emergence.

8.6. Subject Diary

At Visit 2 (Week 0), an investigational center staff member will explain the use of the electronic diary (eDiary) to each subject/caregiver. The eDiary will be used to collect daily information regarding:

- Study medication application frequency compliance
- Blister lancing compliance
- New lesions that develop in between study visits
- Bandage use
- Use of routine cleansers
- Pruritus Severity
- Pain Severity
- Mobility

At Visit 2 an investigational center staff member will register each subject who is randomized into the eDiary in the IRT system.

At Visits 3-7 an investigational staff member will reinforce the instructions for proper use of the eDiary with each subject/caregiver. Specifically, staff will ensure each subject/caregiver understands the palmar method for BSA% measurement to estimate new lesions that develop in between study visits and record the information in the eDiary. Staff will also emphasize the importance of not exceeding 30% BSA being treated at any time throughout the treatment period of the study.

Instructions for use of the IRT system will be provided to each investigator prior to the initiation of subject enrollment at her/his center.

8.7. STUDY DURATION

The duration of study participation for a subject is anticipated to be a maximum of 158 days. This includes the up to 6-week screening period, an 8-week treatment period and an 8-week no-treatment follow-up period. The final study visit (Visit 8/Week 16) has a maximum allowable visit window of 4 days.

The study end date is the date of the last subject's last visit.

8.8. STUDY MEDICATIONS

8.8.1. Study medication identity

The study medications are yellow ointments that are indistinguishable in physical appearance. The study medications must be stored in a secure area with limited access under appropriately controlled and monitored storage conditions.

Study Medication Information		
Study medication name	Diacerein (CCP-020) 1% Ointment	Control Ointment
Manufacturer	TWi Pharmaceuticals, Inc., Taoyuan City, Taiwan	
Diacerein concentration (%)	1	0
Pharmaceutical Form	Ointment	
Storage Conditions	59°F to 86°F (15°C to 30°C)	
Dose regimen		
Route	Topical	
Frequency	Once-daily application to all EBS lesions	
Duration of administration	Once-daily applications for 8 weeks	

8.8.2. Study medication formulation

	Ingredients	Function	Specification	Proposed Clinical Trial Formulation (% w/w)
Diacerein (CCP-020) 1% Ointment	Diacerein	Active	EP monograph 2409	1.0
	Mineral oil, light, NF	Ointment base	NF	12.0
	Petrolatum, white, USP	Ointment base	USP	84.5
	Cetyl alcohol, NF	Thickener	NF	2.0
	Ethylparaben, NF	Preservative	NF	0.5
Control Ointment	FD&C Yellow #5, AL 15% - 17%, Aluminum Lake (5175)	Colorant	EU 231/2012	0.025
	Mineral oil, light	Ointment base/ skin protectant	NF	12.0
	Petrolatum white	Ointment base/ skin protectant	USP	85.475
	Cetyl alcohol	Thickener	NF	2.0
	Ethylparaben	Preservative	NF	0.5

8.8.3. Study medication packaging and labeling

The study medications are yellow colored ointments and will be packaged in identical appearing, aluminum tubes that each contain 30 grams of study medication.

A bulk supply of each study medication, with one tube in each carton, will be provided to each investigational center. A sufficient supply of study medication will be provided to each site prior to the initiation of subject enrollment and replenished as needed.

Each carton will be labeled with a two-part label. One part of the label remains attached to the carton, the other part (tear-off) is separated and attached to the subject's drug accountability log when the tube is dispensed.

Both parts of the carton label show at least the following:

- Tube number
- Protocol number
- Storage conditions
- Instructions for use
- Sponsor information
- Investigational drug warning
- Space to enter site number
- Space to enter subject number.

Each study medication tube will be labeled with a one-part label that remains attached to the tube and shows at least the following:

- Tube number
- Protocol number
- Investigational drug warning
- Space to enter site number
- Space to enter the subject number.

8.8.4. Method of treatment assignment

Prior to the start of the study, Castle Creek Pharmaceuticals, LLC or a designated third party will generate a list of randomization numbers that shall be transmitted to the assigned clinical packaging organization for study medication labeling.

The randomization list will be stored with access limited to designated personnel for study medication labeling. The randomization list will be made available as appropriate to un-blind the database.

8.8.5. Dispensing study medication

The study medication must be dispensed only to study subjects, only at investigational centers specified on the Form FDA 1572 (or its equivalent) and only by authorized personnel as required by applicable regulations and guidelines.

The subject/caregiver must bring dispensed study medication tubes and, if possible, cartons with them to all visits.

At Visit 2 (Week 0), after the subject is randomized and the assigned study medication tubes have been identified an investigational center staff member will weigh each tube of study medication (without the carton and with the cap) to the nearest 0.1 gram then give the tube(s) and the carton(s) of study medication to the subject/caregiver.

An investigational staff member will also weigh the study medication tube used for the first study medication to the nearest 0.1 gram after the application.

At Visits 3-5, examine the tube(s) of study medication dispensed to the subject/caregiver, and weigh each opened tube of study medication (without the carton and with the cap) to the nearest 0.1 gram.

Collect tubes and cartons that do not contain a useable amount of study medication. Weigh the returned study medication tubes (without the carton and with the cap).

Dispense an appropriate number of study medication tubes with cartons to the subject/caregiver. Weigh each tube of study medication (without the carton and with the cap) to the nearest 0.1 gram.

At Visit 6 (Week 8), collect all study medication tubes and, if possible, cartons from the subject/caregiver and weigh all the tubes (without the carton and with the cap), whether they were opened or not, to the nearest 0.1 gram.

The investigational center staff should make every effort to obtain all dispensed and unused study medication. Two documented telephone contacts followed by a registered letter to the subject/caregiver are adequate follow-up efforts. If these efforts fail, the reason for the failure must be noted in the eCRF. All unused and un-dispensed study medication should be held for inspection by the monitor. Upon completion of the study, all study medication will be returned to Castle Creek Pharmaceuticals, LLC or a designated third party by the monitor using a traceable method.

8.8.6. Study medication application

The study medications are for external, topical use on the subject's EBS lesions only.

At Visit 2 (Week 0), an investigational center staff member will instruct the subject/caregiver on the appropriate application technique. The subject/caregiver will perform the first study medication application and a staff member will observe the application. The staff member must ensure the study medication tube is weighed before AND after the first application.

To perform a study medication application, the subject/caregiver should:

- Wash her/his hands before starting the application
- Apply sufficient quantity of the assigned study medication to cover all EBS lesions and to about ¾ inch (2cm) of uninvolved skin surrounding each lesion with a thin layer and gently rub it in
 - A general rule to follow is 1 fingertip unit of study medication is sufficient to cover approximately 1 % BSA (palmar method measurement) for that particular subject
- Not cover the treated area with any type of bandage or dressing for 1 hour after the application
- Wash her/his hands after completing the application.

At Visit 2 a staff member should monitor the subject for at least 20 minutes after the first application to detect any immediate adverse events.

8.8.7. Dose compliance record

Each subject/caregiver will record the subject's compliance with the study medication application frequency on a daily basis in an eDiary.

8.8.8. Dose modification

Subjects/caregivers should not modify the study medication application procedure or frequency without approval from the investigator or designee.

If any significant study medication intolerance or safety issue occurs the investigator or designee may direct the subject/caregiver to reduce the study medication application frequency as determined by the Investigator.

If the subject does not apply the study medication once daily to the assessment area for more than seven consecutive days, the subject must be removed from the study.

Moderate-to-severe diarrhea has been observed in some patients administered oral diacerein for the treatment of osteoarthritis:

- Moderate diarrhea: 5-10 watery stools per day
- Severe diarrhea: >10 watery stools per day.

Study medication applications should be discontinued if the subject experiences moderate or severe diarrhea.

Study medication should also be discontinued if the subject experiences any instance of diarrhea with bleeding and there is no clear medical rationale for the occurrence.

The diarrhea must be reported as an adverse event in the eCRF. These subjects should be withdrawn from the study.

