6. INVESTIGATIONAL PLAN

6.1. Overall Study Design

This is an international, multi-center, randomized, double-blind, parallel group study to evaluate the safety and efficacy of topical Diacerein 1% Ointment for the treatment of subjects with EBS. Subject randomization will be stratified by genotype (KRT5 and/or KRT14 versus other genotype) and age group (<8 and ≥8 years old). Subjects will be screened for inclusion and exclusion criteria at Visit 1 (Week -6). Subjects must have a genotypic confirmation of EBS (or have a blood or saliva sample collected for genetic confirmation). At Visit 2 (Week 0) eligible subjects will be randomized in a 1:1 ratio to either receive 8 weeks of once-daily application of Diacerein 1% Ointment or Control Ointment to all EBS lesions in the Assessment Area except plantar areas where >25% of the area has hyperkeratosis that has been present for greater than 12 weeks and the scalp, groin and areas where, in the investigator's opinion, the study medication might become occluded are excluded. At Visit 2 (Week 0) all subjects or their caregivers (subjects/caregivers) will be instructed on the daily study medication application technique. For each application, a thin layer of the assigned study medication, sufficient to cover the lesion and approximately ¾ inch (2 cm) of surrounding uninvolved skin, will be applied and gently rubbed in. Subjects/caregivers will apply the assigned study medication to all EBS lesions, including any new lesions that develop, provided that the area being treated does not exceed 30% BSA during the 8-week treatment period. At Visit 2 (Week 0, baseline) the subject's first study medication application will be observed by a member of the study staff. Subsequent study medication applications will be performed by the subject/caregiver. The application technique will be reviewed with subjects/caregivers at all treatment period visits. No study medication applications will be made to any lesion that becomes infected until the infection resolves with appropriate investigational center specific medical care.

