7.6. Infected Lesions

EBS lesions that become infected (*i.e.*, EBS lesions that require therapy to treat an infection) during the course of the study should be managed following the investigator's routine practice and all concomitant therapies reported in the eCRFs.

No study medication applications should be made to infected lesions. If any EBS lesions are not treated with study medication because they are infected, this situation must be noted as an adverse event. If the subject does not apply the study medication once daily to all EBS lesions for more than seven consecutive days, the subject must be withdrawn from treatment.

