7.7. Subject Discontinuation from the Study

Subjects/caregiver will be informed that the subjects are free to withdraw from the study at any time and for any reason. Subjects also have the option to withdraw from treatment at any time. Subjects that withdraw from treatment will continue to follow their visit schedule but will no longer apply the study medication.

The investigator may remove a subject from the study if, in the investigator's opinion, it is not in the best interest of the subject to continue the study. If the subject does not apply the study medication once daily to all EBS lesions for more than seven consecutive days, the subject must be withdrawn from treatment.

Examples of other reasons subjects may be discontinued from the study are:

- A change in compliance with an inclusion or exclusion criterion
- Occurrence of AEs
- Occurrence of pregnancy
- Use of a prohibited therapy
- Failure to maintain the required application frequency.

In case of premature discontinuation of study participation, efforts will be made to perform all final study day assessments. The date the subject is withdrawn from the study and the reason for discontinuation will be recorded on the subject's eCRFs. All withdrawn subjects with ongoing AEs will be followed as appropriate.

The investigator must immediately (within 24 hours) notify the Castle Creek Pharmaceuticals, LLC assigned study monitor of a subject discontinuation.

The study may be discontinued at the discretion of Castle Creek Pharmaceuticals, LLC. Some examples of reasons for discontinuation are the occurrence of the following:

- Increased frequency, severity or duration of known AEs
- Medical, regulatory or ethical reasons affecting the continued performance of the study
- Difficulties in the recruitment of subjects.

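### The seven-day non-application rule stops treatment in Sections 7.6 and 7.7 but ends study participation in Section 8.8.8, which can turn a subject into a Week 8 non-responder

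*Protocol*

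**What the plan says.** Protocol Section 7.6, repeated in Section 7.7, covers the subject who does not apply medication "once daily to all EBS lesions for more than seven consecutive days, the subject must be withdrawn from treatment". Section 7.7 says what follows: "Subjects that withdraw from treatment will continue to follow their visit schedule but will no longer apply the study medication".

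Protocol Section 8.8.8 covers the subject who does not apply it "once daily to the assessment area for more than seven consecutive days, the subject must be removed from the study". For premature discontinuation of study participation, Section 7.7 offers only that "efforts will be made to perform all final study day assessments". The same section lists "Failure to maintain the required application frequency" among examples of reasons why a subject may be discontinued from the study.

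Two provisions on permitted non-dosing sit beside these rules. In Section 8.8.8, for intolerance or a safety issue, "the investigator or designee may direct the subject/caregiver to reduce the study medication application frequency as determined by the Investigator". In Section 7.6, "No study medication applications should be made to infected lesions", and Section 6.1 describes the same hold: "No study medication applications will be made to any lesion that becomes infected until the infection resolves".

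The SAP keeps every randomized subject who was dispensed medication in the ITT population (Section 4.1). It counts unknown Week 8 status as non-response for the primary BSA endpoint (Sections 5.5 and 7.1) and for the key secondary IGA endpoint (Section 7.2). The per-protocol population requires a Week 8 BSA and IGA (Section 4.3). The list of changes from the protocol in SAP Section 12 does not mention the seven-day rule.

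**The concern.** Both versions are mandatory, and a subject who stops dosing entirely for eight days meets both triggers. A site that follows Section 7.7 stops the ointment and still sees the subject at Visit 6. A site that follows Section 8.8.8 discharges the subject. The two sites can then report different primary outcomes for the same clinical course: one from the skin as seen at Week 8, the other from the missing-data rule.

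The outcome is lost because of a choice between two protocol sections, not because the subject declined follow-up. The loss affects both confirmatory endpoints, and the per-protocol analysis drops the subject as well.

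**Working it through.** **1. The two rules side by side**

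| | Sections 7.6 and 7.7 | Section 8.8.8 |
|---|---|---|
| Trigger | Not once daily to all EBS lesions for more than 7 consecutive days | Not once daily to the Assessment Area for more than 7 consecutive days |
| Consequence | Treatment stops | Study participation ends |
| Later visits | Continue as scheduled | Best-effort final assessments only |
| Week 8 BSA and IGA | Still collected | May be missing |
| Scoring at Week 8 | Observed data | Non-responder if unknown |

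Neither document ranks the rules.

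**2. When it matters.** The first application is observed on Day 1. A gap starting on Day 2 reaches its eighth missed day on Day 9, so removal is possible from Day 9. Visit 6 is due on Day 57, and treatment ends there. A removal between those dates can cost the Week 8 value.

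**3. Size per subject.** SAP Section 11 plans 80 subjects, allocated 1:1, so 40 per arm. One responder rescored as a non-responder moves that arm by 1/40 = 2.5 percentage points. A removed subject who would not have responded moves it by 0.

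**4. The plan's own power figure.** Inputs from SAP Section 11: p1 = 0.60, p2 = 0.30, n = 40 per arm, two-sided alpha = 0.049 (z = 1.969). With pooled variance under the null:

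power = Φ( [d − z·√(2·p̄(1−p̄)/n)] / √([p1(1−p1) + p2(1−p2)]/n) )

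Here d = 0.30 and p̄ = 0.45. The null term is 1.969 × √(2 × 0.2475/40) = 0.219, and the denominator is √(0.45/40) = 0.106. Power is 77.7%, against 77% stated, so the figure reproduces.

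**5. Illustration only.** Suppose k subjects per arm are removed before Week 8. If they would have responded at their arm's planning rate, each rate becomes p × (1 − k/40):

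| k per arm | Rates | Power |
|---|---|---|
| 0 | 0.600 / 0.300 | 77.7% |
| 1 | 0.585 / 0.2925 | 75.8% |
| 2 | 0.570 / 0.285 | 73.7% |
| 4 | 0.540 / 0.270 | 69.5% |

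Subjects who stop dosing may respond less often. At half the planning rates and k = 4, keeping them gives (36 × 0.60 + 4 × 0.30)/40 = 0.570 against (36 × 0.30 + 4 × 0.15)/40 = 0.285, which is 73.7% power. Removing them gives 69.5%. If none would respond, keeping or removing them gives the same result.

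The values of k are assumptions, since the documents give no rate of seven-day gaps. The 60% and 30% rates were set for a 40% BSA reduction at Week 16; SAP Section 11 says no data exist for the current 60% reduction at Week 8.

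**The case against.** The strongest reply is that the harm is smaller and less certain than the conflict suggests. Several stronger readings are tempting and are not supported.

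- **Infection holds.** A reader might infer that one infected lesion on hold for eight days makes the subject a failure. The broad trigger that catches a single held lesion is in Sections 7.6 and 7.7, where visits continue and Week 8 data are kept. A subject who holds one lesion and doses the rest is still applying medication to the Assessment Area, unless Section 8.8.8 is read very strictly. Section 7.6 states the seven-day limit straight after the hold, so it may be a deliberate cap.
- **Directed reductions.** The removal sentence follows directly after the permission to reduce frequency, so a permitted reduction could be read as ending participation. It can equally be read as covering only unapproved gaps. This is an ambiguity to close, not a second contradiction.
- **The bullet in Section 7.7.** It is a discretionary example, not a third mandatory rule.
- **Certain loss of the Week 8 value.** Section 7.7 asks for final assessments, and an exit close to Visit 6 might supply a value. The nearest-visit rule in SAP Section 5.2 does not settle this, because it is written for descriptive and summary statistics.
- **A bias in a known direction.** Removals concentrated in one arm would distort the comparison, but the documents link this rule to neither arm.

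It is also fair to say that SAP Section 5.5 plans two opposite extreme-case analyses and a multiple imputation, and that SAP Section 6.1 tabulates reasons for withdrawal. These show how much missing outcomes could matter, but they do not recover them. What remains is the conflict over the consequence, and its path to both confirmatory endpoints.

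**Conclusion.** The point holds in this form: the same dosing gap leads to treatment withdrawal in one place and study removal in another, nothing says which governs, and the second route can replace an observed Week 8 outcome with an assigned failure.

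The conflict itself is certain. Its effect on the result is not known. The firm figure is 2.5 percentage points in an arm of 40 for each would-be responder lost, and zero for a removed subject who would not have responded. The power figures above show sensitivity under assumed removal counts and superseded planning rates; they are not a forecast, and a reader should not take any of them as the expected loss. The text should be corrected because the rule is wrong as written and the outcomes it can lose are avoidable.

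**What to change.** 1. In Section 8.8.8, replace removal from the study with: *withdrawn from treatment, and will continue all scheduled visits and assessments*.
2. Use one trigger in Sections 7.6, 7.7 and 8.8.8: no once-daily application to the Assessment Area for more than seven consecutive days.
3. State in Section 8.8.8 that a frequency reduction directed by the investigator does not trigger the rule.
4. In Section 7.7, list the application-frequency bullet as a reason for treatment withdrawal, not study discontinuation.

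Whether an infection hold longer than seven days should stop all treatment is an exposure and safety decision for the sponsor; whichever way it goes, the text should say so. The separate diarrhea instruction in Section 8.8.8 is not affected.

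The cost is wording in the protocol amendment that SAP Section 12 already foresees. Sample size and alpha do not change, and retained subjects attend visits already scheduled. The drawback is that less-exposed subjects contribute observed outcomes, which may dilute the estimated effect; that is consistent with an intention-to-treat analysis.
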